4.3 ANALYSIS OF STUDY CONDUCT

The following analyses of study conduct will be carried out on the safety population or mITT, as appropriate.

The patients excluded from each analysis population will be summarized, including the reason for exclusion.

A summary of enrollment by country and investigator site will be produced.

The number of patients who completed or discontinued from the study by Week 52, including the reason for discontinuation, will be summarized by treatment group.

A listing of early withdrawals will be produced.

A summary of the number of patients who entered the study and who failed to meet all inclusion/exclusion entry criteria will be produced. Major protocol deviations will be listed and summarized.

Patient duration in the 52-week treatment period will be summarized. Duration will be calculated as:

date of last visit – date of the first dose +1

Previous and concomitant medications will be summarised descriptively by mapped term and treatment group. A summary of rescue medications for PV will also be produced.

A summary of the number of patients who experience treatment failure along with the reason(s) for treatment failure will be produced. The number of patients receiving rescue will also be listed and summarised.

A summary of exposure to study treatment will be produced using the dose recorded on the electronic case report form (eCRF). The number of RTX/placebo RTX infusions and dose received at each infusion and overall will be summarised by treatment group. The mean daily dose, total cumulative dose, and duration of treatment of MMF/placebo MMF over the 52-week treatment period will be summarised.

4.4 ANALYSIS OF TREATMENT GROUP COMPARABILITY

Summary tables will be produced for the safety population for baseline demographic and disease characteristics. If it is found that there is a large difference in the number of patients in the safety population compared to the ITT population, additional summaries will be produced based on treatment as randomized.

Demographic and baseline disease characteristics will be summarized as described in the following sections.

Rituximab—F. Hoffmann-La Roche Ltd
13/Statistical Analysis Plan WA29330

4.4.1 Demographics

Demographics will be summarized, including:

- Gender (male/female)
- Age (years)
- Height (cm)
- Weight (kg)
- Body mass index (kg/m²)
- Race
- Ethnicity
- Geographic region
- Smoking status
- Female reproductive status

4.4.2 Disease Characteristics

Baseline values will be summarized, including:

- Duration of PV (months)
- Prednisone dose (mg/day)
- Overall PDAI total activity score
- Site of disease (mucosal only, mucocutaneous, cutaneous only. Site of disease will be determined as follows:
 - Mucosal only: PDAI total mucosal activity score>0 and PDAI total skin activity score = 0 and PDAI total scalp activity score=0
 - Cutaneous only: PDAI total mucosal activity score=0 and at least one of PDAI total skin activity score or PDAI total scalp activity score is>0
 - Mucocutaneous: PDAI total mucosal activity score>0 and at least one of PDAI total skin activity score or PDAI total scalp activity score is>0
- Anti-Dsg-1
- Anti-Dsg-3
- CD19
- Prior MMF treatment
- Prior RTX treatment

In addition, any clinically significant ECG or chest X-ray abnormalities at baseline will be listed using the safety population.

Medical history data, including surgery and procedures, and baseline conditions will be summarized descriptively by treatment group using the safety population. A glossary

Rituximab—F. Hoffmann-La Roche Ltd
14/Statistical Analysis Plan WA29330

showing the mapping of investigator verbatim terms to diseases will be produced for the medical history data.

4.5 DATA-CUT FOR ANALYSES

For each patient, the day of first dose of study treatment will be designated study day 1. Each subsequent assessment point will be assigned a study day calculated as:

date of assessment – date of first dose+1.

Data beyond the Week 52 visit will not be included in the primary Week 52 CSR. For each patient, data will be cut-off and reported up to and including the earliest of the following:

- Week 52 visit (using upper visit window of Day 364+10 days)
- Date of early withdrawal

Patients who complete the 52-week treatment period but have a missing Week 52 visit, or where the Week 52 visit falls outside the reporting cut-off will be evaluated up to study Day 365 for all analyses involving a duration or exposure element. In such analyses, any references to Week 52 throughout this SAP will imply study day 365 for these patients.

Although SFU data will not be included in data displays for the Week 52 primary reporting event, any deaths at the time of the data-cut, occurring in SFU will be highlighted in the CSR.

4.6 VISIT WINDOWS

In general, data for assessments that are collected by scheduled visits will be mapped to visits that appear in the schedule of assessments per the protocol using the actual study day of assessment. Data mapped to scheduled visits will include all data collected up to the reporting cut-off date, and may include withdrawal visits and unscheduled visits.

Data will never be mapped to visits for which the assessment was not scheduled in the protocol (i.e., results for an assessment conducted at an unscheduled visit will be mapped to the appropriate visit at which the assessment was scheduled). Visit windows will be continuous from the midpoint between two consecutive study visits, and will be dependent on the schedule of assessments for each variable independently. An example of the DLQI visit window is given in [Table 1](#). Visit windows for each variable will be constructed in the same manner.

Table 1 Time Windows of Study Days to Assign Study Visit (for DLQI)

Study Visit	Scheduled Study Day (±3 days)	Time Window (Days)
Baseline	1	≤1
Week 12	84	>1 to ≤126
Week 24	168	>126 to ≤224
Week 40	280	>224 to ≤322
Week 52	364	>322 to ≤375

DLQI = dermatology life quality index.

Derived variables such as remission endpoints or assessments that are collected on an ongoing basis, such as flares and oral corticosteroid dose, will be presented using appropriate time intervals.

Data displays that are presented by visit will only include visits at which the assessment was scheduled to be collected. The methods for handling multiple values within a visit window are described in Section 4.10.3.

4.7 EFFICACY ANALYSIS

The primary and the first five ranked secondary endpoints (listed below) will be tested at an overall 5% significance level using two-sided hypothesis tests. The remaining secondary endpoints will be considered exploratory (Section 2.2.4) and not tested for significance.

To control for overall Type I error, the hypothesis testing on study endpoints will be conducted sequentially starting with the primary endpoint at 5% level of significance. If the null hypothesis relating to the primary endpoint is rejected, the first 5 secondary endpoints will then be tested in a fixed-sequence fashion in the following order:

1. Cumulative oral corticosteroid dose (prednisone or equivalent) over the treatment period
2. Total number of disease flares during the treatment period
3. Time to initial sustained complete remission
4. Time to disease flare
5. Change in health-related quality of life (HRQoL), as measured by the dermatology life quality index (DLQI) score, from baseline to Week 52

If at any step in the testing procedure, the p-value associated with a test is not <0.05, the remaining endpoints below the sequence will not be considered significant.

The mITT population will be the primary population used for the analysis of efficacy outcomes except for duration of sustained complete remission which will be on a subset

Rituximab—F. Hoffmann-La Roche Ltd
16/Statistical Analysis Plan WA29330

of mITT population (see Section 4.7.3.1). Additional analyses will be conducted for sensitivity or exploratory purposes, as described in the relevant sections below.

4.7.1 Primary Efficacy Endpoint

The primary efficacy endpoint is the proportion of patients achieving sustained complete remission during the 52-week treatment period.

The following two-sided hypothesis will be tested at the 5% significance level:

$$H_0: p_{\text{RTX}} = p_{\text{MMF}}$$

$$H_1: p_{\text{RTX}} \neq p_{\text{MMF}}$$

where p denotes the proportion of patients achieving sustained complete remission status.

The primary method for comparing the proportion of patients achieving sustained complete remission will be the Cochran-Mantel-Haenszel test. The analysis will be stratified by the stratification factors applied at randomization. The proportion of patients achieving sustained complete remission in each treatment group will be presented along with the adjusted difference, 95% confidence interval for the difference, and p-value.

4.7.1.1 Sustained Complete Remission

A patient will be considered a responder for sustained complete remission if the following conditions are met for a minimum of 16 consecutive weeks during the 52-week treatment period:

- PDAI total activity score=0
- Prednisone (or equivalent) dose=0 mg/day

Patients who withdraw early from the study or meet the criteria for treatment failure will be evaluated using data up to the point of withdrawal or treatment failure only, whichever occurs first. Patients who are in sustained complete remission at the Week 52 visit will have their duration cut-off at the Week 52 visit for the purpose of calculating the minimum 16 week criteria for the primary analysis, however they will be censored in secondary analyses of duration.

Sustained complete remission is a composite endpoint derived using several sources of information. A description of each variable contributing to the composite endpoint is given below, including methods for data handling and dealing with missing data.

4.7.1.2 Pemphigus Disease Area Index

The PDAI is a scoring system ranging from 0 to 263 and assesses the number and sizes of lesions across cutaneous and mucosal areas of the body, where higher PDAI scores indicate greater disease activity (Appendix 5). The total PDAI score is made up of two components: total activity score (0–250) and total damage score (0–13). The total

Rituximab—F. Hoffmann-La Roche Ltd
17/Statistical Analysis Plan WA29330

damage score measures the extent of post inflammatory hyperpigmentation or erythema from resolving lesions. The trial objective seeks to achieve the absence of new or established lesions (i.e., total activity score=0), with lesser importance being placed on post-inflammatory hyperpigmentation left by lesions that have resolved. For this reason, only the PDAI total activity score will be used for the assessment of sustained complete remission, and will be denoted by PDAI^a throughout this SAP.

For calculating the duration, a patient with a PDAI^a=0 at a visit who fails the criteria at the next visit will be assumed to fail at the date of the visit where PDAI^a=0 was not met. That is, the patient is assumed to maintain the response during the whole interval between the two visits, as any clinically relevant increases in disease activity is expected to be captured by an increase in oral corticosteroids.

Missing Data

Missing PDAI^a scores at a visit will be imputed using the score from the previous or next visit, whichever is higher. If the PDAI^a score is missing at two or more consecutive visits then no imputation will be made, and it will be assumed that PDAI^a>0 for those visits. This imputation will apply for missing overall total scores, and missing anatomical location scores.

4.7.1.3 Prednisone (or Equivalent) Dose

Patients entering the study should receive oral corticosteroids at a prednisone or equivalent dose of 60 or 80mg/day at Day 1. After Day 1, the dose will be tapered to a target dose of 0 mg/day as outlined in the protocol and will be documented in the eCRF. Dose adjustments are tolerated in this trial, however patients inadequately controlled after performing clinically relevant dose adjustments will be considered a treatment failure. Further details for treatment failure are provided in Section 4.2.

Oral corticosteroids will be monitored on an ongoing basis to ensure information is correctly recorded on the concomitant medication page of the eCRF. Any missing or ambiguous data will be queried and all efforts will be made to resolve data issues prior to database lock.

Full details of data handling methods is described in Section 4.7.2.1, this includes reporting conventions for prednisone equivalence and imputation methods for dealing with missing or partial data.

4.7.1.4 Treatment Failure

The primary method for dealing with treatment failures will be to exclude data from the first point a patient meets one of the criteria for treatment failure. The responder status (i.e., responder versus non-responder) for sustained complete remission will be determined using available data up to the point of treatment failure only.

Rituximab—F. Hoffmann-La Roche Ltd
18/Statistical Analysis Plan WA29330

4.7.1.5 Sensitivity Analyses

The primary analysis described in Section 4.7.1.1 will be repeated with the treatment failure criteria relaxed to include patients in whom rescue therapy is initiated. Patients who receive rescue therapy will continue to be analyzed using data up to the point of rescue only; however, patients who meet treatment failure criteria and do not receive rescue therapy will be analyzed using all available data during the 52-week treatment period.

A robustness analysis of patients who withdraw will be conducted using a tipping point analysis. The tipping point is defined as the difference in the number of missing events between the treatment groups that result in a change in the primary outcome conclusions (Yan et al. 2009). A two-dimensional plot will be produced to evaluate where the tipping point lies. The tipping point analysis will be used to assess what the outcome might have been had patients carried on in the trial. All other analysis methods will remain as described for the primary analysis, including the handling of patients who qualify for treatment failure. Patients who experience treatment failure and later withdraw will continue to be analyzed using data up to the point of failure, as this would have been their outcome had they continued in the study.

The primary analysis will also be repeated to include the patients who participated in the trial via TM (10 patients at one investigational site) in order to determine whether the trial conclusions are upheld and independent of the logistics of conducting study assessments, methods of interactions with patients, and method of data collection through TM.

4.7.1.6 Exploratory Analyses

Additional analyses may be carried out, for example:

- Logistic regression analysis to control for additional baseline factors (e.g., PDAI total activity score, prednisone (or equivalent) dose at baseline, location of PV lesions)
- Investigate any effects caused by changes to trial conduct made during the trial, such as changes to the treatment failure criteria between protocol versions 2 and 3
- Further analyses investigating rescue patients who receive an alternative treatment
- Descriptive statistics for the TM subset

4.7.2 Secondary Efficacy Endpoints

Hypotheses related to secondary endpoints will be tested in a fixed-sequence manner for the first five ranked secondary endpoints at the two-sided 5% significance level using the procedure discussed in Section 4.7.

4.7.2.1 Oral Corticosteroids

Oral corticosteroid exposure over the 52-week treatment period will be compared between RTX and MMF using a Wilcoxon Mann-Whitney test, assuming that the data will be non-normally distributed. If it is found that the data follows a normal distribution

Rituximab—F. Hoffmann-La Roche Ltd
19/Statistical Analysis Plan WA29330

using Shapiro-Wilk W Test, a t-test will be used to compare the difference in the two treatment groups.

Oral corticosteroid use over time will be further investigated; this includes data during the screening period. Summaries and plots will be generated, which will include:

- Mean and median daily dose per visit interval with error bars
- Total cumulative dose per visit interval
- Total number of days on oral corticosteroids over the 52-week period
- Categories of mean daily dose per visit interval (e.g., 0 mg/day, 0–<10 mg/day, ≥10 mg/day)

The mean daily dose for a given visit interval will be calculated as follows:

sum of total daily dose across all days in the visit interval ÷ (end date of visit interval – start date of visit interval + 1).

Data presented by specified visit intervals will use all available; if a patient withdraws during a time interval, no imputation will be made for the remaining days in the interval, and only available data up to the time of withdrawal will be used in the calculation. Rescue data will be included in descriptive summaries.

Additional summaries may be produced to investigate corticosteroid use for rescue patients.

A listing showing oral corticosteroid dosing for patients over the 52-week treatment period will be produced using all available data up to the exposure date, with rescue data being flagged.

Data Handling for Oral Corticosteroids

Oral corticosteroids will be recorded in the eCRF under the concomitant medications page. Dose modifications will be tracked by entering the start and stop dates for each dose received. Medications will be flagged as oral corticosteroids using the Sponsor's corticosteroid drug basket and the route administered information as recorded on the eCRF. The Sponsor will review the concomitant medications data on an ongoing basis to ensure medications are being correctly recorded, and are being flagged as appropriate.

For reporting purposes, all relevant oral corticosteroid entries will be standardized by converting to a prednisone equivalent dose, and will be reported under the term 'Prednisone'. A listing of all compounds reported as prednisone will be produced along with the conversion factor applied.

The study management team will monitor oral corticosteroids on an ongoing basis for data quality and to ensure all dose adjustments are being correctly captured. All efforts

Rituximab—F. Hoffmann-La Roche Ltd
20/Statistical Analysis Plan WA29330

will be made to resolve missing or ambiguous data prior to database lock. In the case that data queries cannot be resolved, data will be handled in a conservative manner as described in the sections below.

The intervals for each dose of oral corticosteroid captured during the taper are expected to be continuous and non-overlapping. Patients who are adequately controlled by their blinded treatment may discontinue oral corticosteroids altogether, but may re-start treatment as required to treat any increases in disease activity. With this in mind, the use of available data will be maximized and incorporated into the imputation of missing or partial dates as follows:

Missing Term	Imputation Method
Start Date	
Missing Day	Latest of the following: Previous End Date+1 First day of the month
Missing Month	Previous End Date+1
Missing Year	No imputation
End Date	
Missing Day	Earliest of the following: Next Start Date-1 Last day of the month
Missing Month	Next Start Date-1
Missing Year	No imputation

Within two consecutive dosing intervals, if the end date of the first dose interval is missing and the start date of the second dose interval is missing, a midpoint approach using the start date of the first interval and the end date of the second interval will be used to assign a cut-off end date, providing these dates are available.

A missing or 'ongoing' final end date will be imputed with the exposure date. A missing initial start date will be imputed with Day 1 providing the end date is after Day 1, otherwise no imputation will be made.

If the total daily dose is missing then the dose will be imputed using the dose from the previous dose or the next dose, whichever is higher.

In the event of overlapping dose intervals, the patient will be assumed to be taking the higher dose for the maximum amount of time possible and the lower dose for the minimum amount of time possible within the dates provided, such that the total daily dose will never be double counted.

Rituximab—F. Hoffmann-La Roche Ltd
21/Statistical Analysis Plan WA29330

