2.4 ANALYSIS TIMING

The primary analysis will be conducted when all patients have completed the Week 52 study visit or have withdrawn early from the study. The reporting event for the primary analysis will include data for all patients up to their Week 52 assessment visit within the treatment period, or data up to the point of withdrawal. Safety follow up (SFU) data will not be included within the primary analysis data-cut. All data up to the Week 52 study visit will form part of the Primary Week 52 Clinical Study Report (CSR).

A final reporting event and study database lock will occur after all patients complete the 48-week SFU period or withdraw early from SFU, details of which will be documented in a separate SAP and final CSR. The final CSR will include all available data up to study completion (last patient's last visit [LPLV] in SFU) or early withdrawal from SFU.

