4.2 TREATMENT FAILURE

Treatment failure is the occurrence of any one of the following events:

- After disease control has been achieved, a two-step increase in prednisone (or equivalent) dose to ≥ 20 mg/day for more than 2 weeks to treat increased disease activity during the corticosteroid taper
- Failure to achieve disease control after receiving 240 mg/day oral prednisone (or equivalent) for 1 week

Rituximab—F. Hoffmann-La Roche Ltd
11/Statistical Analysis Plan WA29330

Disease control is defined as the time at which new lesions cease to form and established lesions begin to heal (beginning of the consolidation phase).

- Increase in MMF/matching placebo dosage above 2 g/day
- Initiation of any rescue therapy (addition of another immunosuppressive medication, additional RTX or MMF open-label doses, intravenous (IV) Ig, plasmapheresis, or another treatment or procedure) as determined by the investigator's best medical judgment

The clinical definitions of treatment failure above are aligned with "non-responder" classification for the primary analysis. Patients experiencing treatment failure prior to achieving sustained complete remission will be categorized as non-responders in the primary analysis, but will continue to be followed in the study per the schedule of assessments. Patients who achieve sustained complete remission without experiencing an event constituting treatment failure beforehand will not be categorized as non-responders, regardless of whether they subsequently meet the criteria during the remaining treatment period.

Patients who experience treatment failure will be analyzed using data up to the point of treatment failure for efficacy remission endpoints, including the primary endpoint for sustained complete remission.

From Week 12 through Week 52, patients who experience treatment failure are eligible to receive rescue therapy during the treatment period with another immunosuppressive medication, IV Ig, plasmapheresis, or another treatment or procedure as per the investigator's best medical judgment. An early withdrawal visit is not required for a patient to receive rescue therapy, and patients should continue to be followed in the study per the 52-week treatment period (see [Appendix 1](#)).

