Patients who receive rescue therapy will be evaluated up to the point of rescue only for all main efficacy analyses. Methods for data handling and/or imputing post-rescue data are described throughout Section 4.7. Additional exploratory summaries on key efficacy assessments will be produced that will include rescue data. Safety analyses will include data up to the point of rescue only.

Listings will include all data, including data post-rescue treatment.

Depending on the proportion of patients receiving rescue, patients will be analyzed separately using descriptive statistics for key analyses on study conduct, efficacy, and safety. For relevant summaries, patients may be re-baselined at the time of rescue and data presented as pre- and post-rescue treatment. Rescue analyses will use data as observed. Subject to patient counts, a limited number of analyses may be summarized by type of rescue received (MMF given as rescue, RTX given as rescue, or other).

Rituximab—F. Hoffmann-La Roche Ltd
12/Statistical Analysis Plan WA29330

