4.9.1 Exposure to Study Medication

The number and percentage of patients who received RTX will be summarized by treatment course, along with summary statistics for the dose of RTX received at each infusion and overall.

Duration of rituximab exposure will be calculated as:

- exposure date – date of first rituximab infusion + 1 where exposure date is the earliest of the following:
 - Week 52 visit (using upper visit window of Day 364+10 days)
 - Date of early withdrawal

RTX exposure data will be determined using the dosing information as recorded on the RTX administration log on the eCRF and the actual treatment received as per IxRS. Exposure to RTX will not include RTX given as rescue, which will be analyzed separately.

MMF exposure data will be determined using the dosing information as recorded on the MMF administration log on the eCRF and the actual treatment received as per IxRS.

Exposure to MMF will be calculated as:

- date of the last MMF administration – date of the first MMF administration + 1

Exposure to MMF will not include MMF given as rescue, which will be analyzed separately.

The total cumulative dose will be calculated by summing the total daily dose over the treatment duration. Average daily dose will be calculated as:

- total cumulative dose ÷ treatment duration

Rituximab—F. Hoffmann-La Roche Ltd
30/Statistical Analysis Plan WA29330

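### Cumulative corticosteroid dose, the first ranked secondary, is tested as a 52-week sum that in effect stops at withdrawal or rescue; the SAP gives no rule for the days after

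*SAP*

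**What the plan says.** SAP 4.7 ranks cumulative oral corticosteroid dose first of five secondaries in a fixed sequence after the primary endpoint, so a non-significant result here closes the other four. For the test, SAP 4.7.2.1 states: "Oral corticosteroid exposure over the 52-week treatment period will be compared between RTX and MMF using a Wilcoxon Mann-Whitney test". A t-test replaces it if a Shapiro-Wilk test finds the data normal. There is no stratification, and the section never says how days after withdrawal or rescue enter the tested total. Its withdrawal sentence, "only available data up to the time of withdrawal will be used in the calculation", is about the by-interval summaries.

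Rules elsewhere settle the matter:

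- SAP 4.5, for each patient: "data will be cut-off and reported up to and including the earliest of the following", namely the Week 52 visit or the date of early withdrawal.
- SAP 4.7.2.1, on a missing or ongoing last dose record: the "final end date will be imputed with the exposure date". The term is defined only in SAP 4.9.1, under rituximab exposure ("where exposure date is the earliest of the following"), with the same two dates.
- SAP 2.4: "Safety follow up (SFU) data will not be included within the primary analysis data-cut".
- SAP 4.2: "Patients who receive rescue therapy will be evaluated up to the point of rescue only for all main efficacy analyses". Section 4.7.2.1 admits rescue data only to descriptive summaries.

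The cut at treatment failure is narrower. Those patients "will be analyzed using data up to the point of treatment failure for efficacy remission endpoints", which does not include this endpoint. A patient who fails from Week 12 without rescue is therefore not truncated here.

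**The concern.** Protocol 6 leaves imputation of missing data to the SAP, and SAP 4.10.4 says that Section 4.7 covers it for efficacy. For this endpoint, Section 4.7 covers only missing dates and doses within existing records. A sum that ends at exit with nothing imputed treats every later day as steroid-free. Someone who leaves in Week 4 still on 30 mg/day can then look like one of the best outcomes for steroid sparing.

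This also runs against the section's own approach, which is to handle unresolved steroid data conservatively and to take the higher neighbouring dose when a dose is missing. Early exit is foreseeable: Protocol 3.1.1 requires an early withdrawal visit for treatment failure before Week 12, and the sample size makes no allowance for dropout. At stake are the power and fairness of the first ranked test and access to the four tests behind it.

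**Working it through.** **1. The plan's own figure.** No power or expected value is given for this endpoint. The only design calculation is for the primary endpoint (SAP 2.3: 61 per arm, 40% v 65%, about 80% power). Under the null, SE = √(2×0.525×0.475/61) = 0.0904. Under the alternative, SE = √((0.40×0.60+0.65×0.35)/61) = 0.0875. Power = Φ((0.25−1.96×0.0904)/0.0875) = 79.7%, which reproduces it. The 61 per arm is used below.

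**2. Taper totals.** Doses and durations come from Protocol Table 1 (SAP Appendix 4), with no disease activity.

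- 60 mg start: 7×(60+40) + 14×(30+20+15+12.5+10+7.5+5+2.5) = 2,135 mg.
- 80 mg start: 2,135 + 7×80 = 2,695 mg.

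| Leaves on schedule at | 60 mg start | 80 mg start |
|---|---|---|
| Week 4 | 1,120 mg (52%) | 1,470 mg (55%) |
| Week 8 | 1,610 mg (75%) | 2,065 mg (77%) |
| Week 12 | 1,925 mg (90%) | 2,415 mg (90%) |
| Week 16 | 2,100 mg (98%) | 2,625 mg (97%) |

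The percentages are of the lowest total that a completer following the taper from the same starting dose can reach. By Week 12 the shortfall is about 10%.

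**3. Early leavers who do not rank low.**

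- 240 mg route: 7×(80+120+240) = 3,080 mg by Week 3, or 7×(60+80+120+240) = 3,500 mg by Week 4.
- Two steps back after Step 5, which adds 7×40+14×30 = 700 mg: 1,400+700 = 2,100 mg by Week 9 (60 mg start), or 1,960+700 = 2,660 mg by Week 10 (80 mg start). Both are close to an uninterrupted completer's total.
- An 80 mg starter leaving on schedule after Week 9 has 2,170 mg, above a 60 mg starter's complete taper.

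Their own 52-week dose is still understated if steroids continue after exit.

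**4. Effect on the test (illustrative).** Withdrawal rates, exit times, disease-activity probabilities and effect size are all assumed. The simulations apply Table 1 to 61 patients per arm with a two-sided 5% Mann-Whitney test. Power of simulation A is about 82% on full Day 364 totals; simulation B models some details differently.

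| Leaving, rituximab v MMF | A: exits Weeks 1-51 / 2-24 / 2-16 | B: exits Weeks 2-16, truncated v full |
|---|---|---|
| 10% v 10% | 76 / 75 / 72% | 65% v 77% |
| 20% v 20% | 72 / 66 / 60% | 53% v 75% |
| 5% v 10% | 74 / 65 / 60% | 55% v 76% |

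If rituximab loses more, power hardly changes (82-84% at 10% v 5% in A).

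With no true difference, A rejects 4.6-5.7% of the time when 10-20% leave each arm equally, and 4.9-6.8% with gaps of 4-5 points. A third simulation, with all exits in Weeks 2-11, gives about 5% at 10% v 10%, 7-8% at 0% v 5% and 13-15% at 0% v 10%. The excess favours the arm that loses more patients.

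**5. Stratification and the switch.** The primary test, the flare-rate model, both log-rank tests and the DLQI model all account for region and duration of illness. Of the six gated tests, only this one does not. The Shapiro-Wilk rule gives neither a level nor the sample (pooled or per arm). In simulation the t-test would be triggered in 0.3-5% of trials if pooled, or 0.8-10% if both arms must pass.

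**The case against.** **A to-exit total is a legitimate estimand.** Protocol 3.4.1.2 defines the endpoint over the treatment period, and Protocol 3.1.1 starts SFU at discontinuation. This stands in part: the SAP could choose that total. But it has not stated the choice, and the tested quantity is described as 52-week exposure.

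**Stronger readings the documents do not support.** A reader might infer any of the following:

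- *That the SAP scores later days as 0 mg.* It does not say so; that is the arithmetic effect of the rules combined.
- *That every early leaver ranks lowest.* Step 3 of the working shows otherwise. Rescue is available only from Week 12, so it plays no part in the shortfall before then.
- *That the missing time-in-study offset is a defect, because the flare analysis has one.* The taper is front-loaded: a 60 mg starter leaving at Week 4 averages 1,120/28 = 40 mg/day, against 2,135/364 = 5.9 mg/day for an uninterrupted completer. An offset would push the bias the other way.
- *That no sensitivity analysis is planned.* Protocol 6.2.2 and SAP 4.1.4 plan ITT analyses of the efficacy outcomes. These add the telemedicine patients but leave the truncation as it is.
- *That a false steroid-saving claim for rituximab is likely.* Null rejection approaching 31% needs something like 5% v 25% leaving, which no document suggests, and it ignores the gate. Patients leaving before 16 weeks cannot be responders. If rituximab lost 25% early and MMF 5%, unrelated to response, the primary rates would be 0.65×0.75 = 48.75% and 0.40×0.95 = 38%. Primary power would then be about 22%, and this test would often not be reached. If MMF loses more, rituximab loses power.

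**Conclusion.** The point holds within these limits and should be fixed. As written, the SAP ends the tested sum at withdrawal, or at rescue from Week 12, without saying so for this endpoint. Patients who withdraw on schedule before about Week 12 score below even an uninterrupted completer with the same starting dose. That part rests only on Table 1 and the SAP's rules.

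The consequence is some loss of power even with balanced early withdrawal: about 6-10 percentage points with 10% leaving each arm in simulation A, and 12 in B. Imbalanced early withdrawal also biases the comparison. False-positive inflation is small for gaps of 4-5 points. All simulated figures rest on assumed rates and do not account for the gate on the primary endpoint.

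Summaries that include rescue data (SAP 4.2 and 4.7.2.1), and the SFU dose summary by arm, which leaves out rescued patients (SFU SAP 3.2.1 and 3.7.1.1), do not alter the gated test. The primary endpoint is unaffected.

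**What to change.** 1. **Define the total.** In SAP 4.7.2.1, before unblinding, define it as all oral prednisone-equivalent from Day 1 to Day 364 for every mITT patient. For leavers use the prednisone records already scheduled at SFU visits (Protocol Appendix 2). Where none exist, impute within arm, conditional on dose and cumulative dose at exit. Add matching exceptions to SAP 2.4 and 4.5. State that this is an estimand choice, and whether the total is regardless of rescue. If the to-exit total stays as the main test, report the full-period total as a named sensitivity analysis with a delta adjustment of the imputed post-exit dose. The tipping-point method in SAP 4.7.1.5 counts binary events and cannot be reused. SFU SAP section 1 indicates that the primary analysis has been completed; if so, the full-period total can still be reported, labelled as a sensitivity analysis.
2. **Define the test.** Use a van Elteren test stratified by region and duration of illness, and drop the Shapiro-Wilk switch.

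Do not add an exposure-time offset.

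A simulated check of the full-period total (exits in Weeks 2-16, 20 within-arm imputations, one third or all of the leavers lacking records) gave power of 80-81% with 10% leaving each arm, against 71-72% truncated.

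**Cost.** SAP wording and programming, with no new data collection. Leavers' SFU records need earlier cleaning. SFU lasts 48 weeks after exit, so exits from Week 4 on are covered to Week 52 only if the patient attends, and leavers among the last enrolled may lack the final record at the primary lock. Some imputation remains, for example after withdrawal of consent. The total includes treatment given after exit. The stratified test may cost 1-3 points of power if the strata are unrelated to dose.
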